Fiberoptic bronchoscopy with multiple TBLB has become the “gold standard” diagnostic modality for the assessment of lung allograft function and specifically acute cellular rejection (ACR) following lung transplantation. Most lung transplant programs now perform TBLB for graft function surveillance, new onset symptoms, $\geq 10\%$ decrease in FEV1, assessment of a new lung infiltrate on chest imaging, or as a follow-up for acute rejection or CMV pneumonitis (57). Acute rejection is an established risk factor for the development of bronchiolitis obliterans syndrome (BOS), and therefore it has been proposed that early detection and treatment is of paramount importance (58). The relatively high incidence of silent rejection or infection in asymptomatic patients has lent support for routine surveillance protocols (59,60). Surveillance protocols vary widely between transplantation centers since there is little data to guide the frequency of surveillance biopsies. The ACR surveillance protocol in UMMC includes routine bronchoscopy with TBLB at one-month post-transplant and then every three months for one year. Additional bronchoscopies with TBLB are performed based on surveillance TBLB findings, symptoms, or results of pulmonary function tests (PFT) (61). As in the general population, the most common complications of TBLB in lung transplant recipients are bleeding and pneumothorax. Generally, there is evidence that shows a higher propensity for procedure-related bleeding in the post lung and heart-lung transplant population. Once again, the recorded rate of clinically significant lung hemorrhage is highly dependent of the system adopted for grading of the amount of bleeding. In an early study by Chan et al., bronchoscopy data from 83 lung transplant recipients was reviewed retrospectively. The rate of clinically significant procedure-related bleeding, defined arbitrarily as >50 mL blood loss was 1.9% (62). Scott et al. prospectively evaluated the yield and complications of TBLB in 219 procedures on combined heart-lung transplant patients. Blood was recovered by suctioning in approximately 44% of procedures, while the rate of >100 mL procedure related bleeding was recorded at 12.3% (20). Bjørtuft et al. studied the rate of TBLB-related bleeding in 104 procedures in 51 patients, 29 of whom were post lung or heart-lung transplantation. The rate of clinically significant bleeding, arbitrarily defined is more than 20 mL, was 7.7%. No difference in the rate or volume of clinically significant bleeding was observed between transplant and non-transplant patients. Interestingly, screening platelet count and coagulation tests did not predict bleeding risk in this study (63). A prospective cohort study performed at the Johns Hopkins Medical Institutions between 1996 and 1997 evaluated bleeding complications among 38 bronchoscopies in 15 lung transplant recipients and compared them to 659 bronchoscopies in 423 non-transplant patients. In this cohort, lung transplant recipients were shown to bleed significantly more, report post-procedure hemoptysis, and have their procedure terminated prematurely due to bleeding in comparison to the non-transplant patients. Bronchoscopy procedures, including those where TBLB was performed, were significantly longer in transplant recipients. In a logistic regression analysis, worse hemoptysis was associated with lung transplant status, older age, and longer procedure time. As in prior studies, bleeding risk was independent of platelet count, coagulation studies, use of aspirin, and use of immunosuppressive medications (64). The relation between risk of bleeding and procedure time might reflect a technically challenging procedure or in some cases prolongation of the procedure by attempt to control bleeding. Other possible explanations for the increased propensity to bleed among lung transplant recipients include an already inflamed lung tissue from infection, ACR, or BOS or an increase in blood flow to the transplanted lung, particularly in recipients of single lung

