 - 4.10. Moderate to severe pulmonary hypertension as defined by a mean pulmonary artery pressure of >40 mm Hg on right heart catheterization or an estimated pulmonary artery systolic pressure of >62 mm Hg on transthoracic echocardiography, both performed within 1 year of the procedure.
 - 4.11. An additional synchronous procedure with possible bleeding (bronchoalveolar lavage and endobronchial biopsy allowed), unless the additional procedure is to be performed following TBLB.
 - 4.12. Decompensated liver cirrhosis, defined as the presence of clinically significant ascites, clinical evidence of esophageal or gastric varices, or history of bleeding from gastric or esophageal varices.
 - 4.13. Prior history of TBLB-related airway bleeding requiring admission to the hospital or advanced measures to achieve hemostasis, including endotracheal intubation, bronchial blocker application, bronchial artery embolization, or surgical intervention.
5. Exclusion criteria for application of topical epinephrine:
 - 5.1. Systolic heart failure with an ejection fraction (EF) of <35% as assessed by echocardiography performed within one year prior to the procedure.
 - 5.2. Myocardial infarction, acute coronary syndrome, percutaneous coronary intervention, or coronary artery bypass surgery within 6 months prior to the procedure.
 - 5.3. Symptoms and/or ECG findings suggestive of ongoing cardiac ischemia on the day of the procedure.
 - 5.4. Moderate- to severe-grade cardiac valvulopathy as assessed by echocardiography performed within one year prior to the procedure.

- 5.5. Inadequately controlled supraventricular arrhythmia, including atrial fibrillation, atrial flutter, and atrio-ventricular node re-entrant tachycardia (AVNRT) as revealed by ECG or cardiac monitoring at the time of the procedure.
- 5.6. Presence of an internal cardioverter/defibrillator.
- 5.7. History of second or third degree (complete) heart block or sick sinus syndrome.
- 5.8. Baseline ECG or cardiac monitoring revealing frequent occurrence (≥ 10 events per minute) of atrial or ventricular ectopy documented prior to or at the time of the procedure.
- 5.9. History of ventricular arrhythmias requiring pharmacologic or electrical cardioversion within the 60 days preceding the procedure.
- 5.10. Serum potassium of <3.0 mmol/L within the week prior to the procedure.
- 5.11. Serum glucose level of ≥ 300 mg/dL within the week prior to the procedure.

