Informed Consent will be performed on the day of study recruitment. Eligible PROPHET Study patients will be discretely approached by one of the study investigators who will explain in layman's language the aims, methods, potential benefits, and hazards associated with participation in the PROPHET trial. Details of the protocol will be discussed with the potential participant at the time of scheduling the bronchoscopy procedure, ensuring adequate time for consideration of the protocol (>24 hours from initial discussion). These individuals will then be approached with the informed consent form. Whenever possible, the informed consent form will be given to the potential participants in advance. The risks, benefits, and alternative will be discussed so that the decision to participate in the study will be made independently by the candidate. Only a well-trained clinical coordinator, the principal investigator, or an associate investigator from the Division of Pulmonary and Critical Care Medicine in UMMC will obtain consent. The consent will be obtained using and Institutional Review Board (IRB) approved consent document.

Any potential participants who cannot consent for themselves will be excluded from the study, as defined by the exclusion criteria (see above). This includes anyone who will be, or will have been, in a stressful, painful, or drugged condition before or during the consent process or otherwise lacks the mental capacity to consent for themselves. We will not obtain consent from Legally Authorized Representatives (LARs). We will not enroll minors.

Lung transplantation recipients undergo multiple bronchoscopic procedures in the post-transplantation period. Hence, it is very likely that a patient who is eligible for participation in the

study will undergo more than one bronchoscopy with TBLB during the study period. In this instance, a separate informed consent will be obtained for each individual procedure.

Initial Evaluation

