Any potential PROPHET participants who meet initial screening criteria and are anticipated to undergo bronchoscopy with TBLB will undergo a thorough chart review conducted by a member of the research team. Demographics, past medical history and comorbid conditions, indication for lung transplant, indication for bronchoscopy with TBLB and possible concurrent procedure(s), prior complications related to bronchoscopy or TBLB, current and active medications, most recent pulmonary function tests, and most recent report of echocardiogram will be reviewed to ensure inclusion and exclusion criteria are met. Recent laboratory data including complete blood count, comprehensive metabolic panel, coagulation studies, and 12-lead electrocardiogram will be reviewed following our institutional standard protocol for bronchoscopy.

On the day of procedure, as per our institutional procedural protocol, participants will have intake vital signs obtained. Recent history and physical examinations dated within 30 days of procedure will be reviewed or obtained if not available. Participants will be monitored under telemetry starting with this intake period, during and approximately an hour after conclusion of procedure unless procedural complication merit additional closer monitoring.

Monitoring Subjects and Criteria for Withdrawal of Subjects from the Study

Before and after the procedure, on the procedure day, study participants will be monitored in the UMMC endoscopy peri-procedure suite (for outpatients) or in the admitting unit (for inpatients). An on-call pulmonary physician will be available to assist with any immediate issues. During the procedure, study participants will be monitored by the UMMC bronchoscopy suite nursing staff, the performing bronchoscopist, and any additional physicians participating in the procedure. We do not anticipate problems requiring withdrawal of patients from the PROPHET study once enrolled, other than by the patient's request. In the event a study subject elects to be withdrawn from the study and requests their data to be withdrawn as well, we will comply.

Study Drug and Placebo Preparation, Packaging, and Randomized Assignment

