As described below, the next step is for a second team member to randomly select one set of labeled syringes without the first study team member knowing which was selected, and then log the selection. As such, the team remains blinded and only when the two logs are later merged will drug assignment be unblinded.

Study Group Randomized Assignment

To eliminate bias, two randomization and blinding processes will be employed: in preparing and labeling the sets syringes (as described above) and in choosing of the set of syringes at the time of the procedure. Those two separate processes will be performed by different members of the research team, each of them blinded to the results of the other procedure:

1. Two syringes will be prepared with the study drug (1:10,000 dilution of epinephrine) and two will be prepared with placebo (sterile saline). The syringes will be randomly labeled "A" and "B" based on a computerized electric coin toss and documented in a separate database as described above. This will be done by a member of the research team who will not be participating in the procedure and therefore blinded to the second randomization (syringe selection).
2. The syringes will be delivered to the procedure room prior to the procedure. At this time, the research team member who is responsible for the syringes will leave the room prior to the second randomization point.
3. The bronchoscopist or his/her assistant who is blinded to the drug and placebo preparation process will randomly choose "A" or "B" based again on a computerized electric coin toss.
4. The chosen set of syringes will be recorded as part of the study database.

Procedure Performance

1. Bronchoscopy will be performed in the controlled environment of the UMMC dedicated bronchoscopy suite under moderate sedation. The bronchoscopy suite in UMMC is routinely staffed by a nurse and a respiratory therapist in addition to the bronchoscopist and any trainees assisting with the procedure.
2. In addition to informed consent for participation in the study protocol, a formal UMMC informed consent for the performance of fiberoptic bronchoscopy, bronchoscopy-related procedures, and use of moderate sedation will be obtained.

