Moderate	Any bleeding originating from the biopsy target airway requiring in addition to maneuvering the bronchoscope application of iced saline or topical epinephrine or placing the patient with the bleeding lung in the dependent position
Severe	Any bleeding originating from the biopsy target airway requiring, in addition to the above-mentioned maneuvers, early termination of the procedure or necessitating application of balloon tamponade, endotracheal intubation, application of a bronchial blocker, or use of other invasive measures to achieve hemostasis, such as bronchial artery embolization or surgical intervention

4. Number of forceps passes performed.
5. Number of adequate tissue samples obtained.

6. Early termination of the procedure due to bleeding complication, defined as non-achievement of the target number of tissue samples as designated by the performing bronchoscopist prior to the procedure related to hemorrhage.
7. Duration of the procedure from first bronchoscope insertion to last bronchoscope withdrawal.
8. Total volume of iced saline used during the procedure.
9. Total dose of unblended topical epinephrine used during the procedure.
10. Any use of hemostatic procedures including balloon tamponade, endobronchial blocker, bronchial artery embolization, emergency surgery.
11. Any use of devices or procedures with intention of securing the airway including oral airway, nasal airway, laryngeal mask, endotracheal intubation, emergency cricothyroidotomy, and emergency tracheostomy.
12. Unplanned admission to the hospital or escalation in level of care within 48 hours of the procedure.
13. Pathologic diagnosis achieved.

Safety Outcomes

The safety of topical epinephrine administration and potential instillation-related adverse events will be derived from clinical monitoring, vital signs, and ECG recordings during and immediately following the procedure as well as from any clinical, laboratory, or radiologic investigations performed during or following the procedure. Complications deemed related to topical epinephrine administration and comprise the study safety outcomes include:

1. All-cause mortality within 3 hours of instillation of the study drug.
2. Acute cardiovascular event, including cardiac arrest, new onset chest pain, acute myocardial ischemia, pulmonary edema, acute ischemic stroke, critical limb ischemia, acute mesenteric ischemia, occurring within 30 minutes of instillation of the study drug.

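### Patients can re-enter and be re-randomised at each biopsy, but no eligibility criterion addresses a safety outcome after an earlier study instillation

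*Combined protocol and SAP*

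**What the plan says.** **Re-entry.** Process of Obtaining Informed Consent expects that an eligible patient will often have more than one bronchoscopy with biopsy during the study, and adds: "In this instance, a separate informed consent will be obtained for each individual procedure". The local surveillance schedule is "routine bronchoscopy with TBLB at one-month post-transplant and then every three months for one year".

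**Assignment.** Under Study Group Randomized Assignment, the syringe sets are labelled by coin toss on the procedure day and the set to be used is then chosen "based again on a computerized electric coin toss". No carry-over of an earlier arm is described.

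**Withdrawal.** Monitoring Subjects and Criteria for Withdrawal states: "We do not anticipate problems requiring withdrawal of patients from the PROPHET study once enrolled, other than by the patient's request".

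**Exclusions.** Only 4.13 is tied to an earlier biopsy: "Prior history of TBLB-related airway bleeding requiring admission to the hospital or advanced measures to achieve hemostasis". The section 5 exclusions apply whatever the cause. Criterion 5.5 bars inadequately controlled supraventricular arrhythmia "as revealed by ECG or cardiac monitoring at the time of the procedure". Criterion 5.9 bars "History of ventricular arrhythmias requiring pharmacologic or electrical cardioversion within the 60 days preceding the procedure".

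**Safety outcomes.** Item 2 covers acute cardiovascular events, including "pulmonary edema, acute ischemic stroke, critical limb ischemia, acute mesenteric ischemia, occurring within 30 minutes of instillation of the study drug". Item 3 is acute closed-angle glaucoma. Item 4 covers ischemic ECG change, new arrhythmia and new conduction block. All use the same 30-minute window.

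**The concern.** The protocol treats its safety outcomes as complications attributable to the instilled epinephrine, yet it has no rule for a participant who has one and returns for the next biopsy. A serious bleed at an earlier biopsy bars re-entry; a serious reaction after an earlier study instillation does not, as such. Taken at face value, the criteria readmit someone who had a stroke or a run of ventricular tachycardia within minutes of blinded study drug, and no independent person is asked whether that is sensible.

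At stake is the safety of individual participants, not the validity of the primary comparison. The protocol itself cites ventricular fibrillation and ST elevation after bronchoscopic epinephrine.

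**Working it through.** The plan gives no figure on this point to reproduce. The check sets each safety outcome (Safety Outcomes, items 2 to 6) against the exclusions and asks whether a participant who has recovered would be barred at the next routine biopsy.

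| Outcome after an earlier instillation | Exclusion that could apply | Barred three months later? |
|---|---|---|
| Myocardial infarction or acute coronary syndrome | 5.2 (6 months) | Yes |
| Second- or third-degree block | 5.7 (no time limit) | Yes |
| Closed-angle glaucoma | 5.16 (1 year) | Yes |
| Critical limb ischemia | 5.12 (no time limit) | Yes, if due to peripheral arterial disease |
| Mesenteric ischemia | 5.12 | Only if attributed to peripheral arterial disease |
| Frequent ventricular ectopy | 5.8 | On one reading only |
| Cardioverted ventricular arrhythmia | 5.9 (60 days); 5.6 if a defibrillator was implanted | No, unless 5.6 applies |
| Ventricular tachycardia not cardioverted | Not met by 5.9 at any interval | No |
| Supraventricular arrhythmia, resolved | 5.5 looks only at the procedure | No |
| Chest pain or ST change without acute coronary syndrome | 5.3 looks only at the procedure day | No |
| Stroke, pulmonary edema, bundle branch block | None for the event itself | No |
| Heart-rate or blood-pressure change, resolved | 5.13 to 5.15 need persistent values | No |

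**Criterion 5.8.** It concerns ectopy of at least 10 events per minute on a baseline ECG or monitoring, documented before or at the procedure, with no look-back limit. The ectopy outcome in item 4 is a rise of at least 10 per minute, so anyone who has it also reaches the 5.8 rate. If documentation before the procedure includes monitoring at an earlier study procedure, 5.8 bars re-entry. If the reference to baseline limits it to the current visit, it does not.

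**Criterion 5.9 against the biopsy schedule.** Three calendar months are 89 to 92 days. 89 − 60 = 29 and 92 − 60 = 32, so the look-back ends 29 to 32 days before the next routine biopsy.

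**Chance of epinephrine at re-entry.** With two independent fair tosses, 0.5 × 0.5 + 0.5 × 0.5 = 0.5.

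**Dose.** 2 mL × 0.1 mg/mL = 0.2 mg per airway; at most two airways give 0.4 mg. The local rescue maximum is 6 mL × 0.1 mg/mL = 0.6 mg.

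**Number affected.** Potential Risks and Discomforts says there are no incidence data for prophylactic use, and the number of repeat entries is not stated. As an illustration only, assume 50 epinephrine procedures (half of 100) and an event rate from 0.1% (the upper figure the protocol cites for topical epinephrine in sinus surgery, a different site) to 2% (assumed). That gives 50 × 0.001 = 0.05 to 50 × 0.02 = 1 event. Only events that escape the exclusions and are followed by re-entry matter here. Events after placebo and sedation would be additional.

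**The case against.** The strongest reply is that an exclusion list is a minimum. A reader might infer from the withdrawal sentence that an investigator may not remove a participant, or must re-enrol one. The text says neither. Each entry is a single session with a short-acting drug, so re-entry is a question of eligibility, and that sentence is not itself the fault.

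Several steps would bring an earlier event to attention. Initial Evaluation includes chart review of earlier bronchoscopy complications, eligibility is reviewed again on day 0, and consent is repeated. A likely related event needing intervention goes to the IRB within 5 business days. Non-serious unanticipated problems go within 14, which is 18 to 20 calendar days and so normally before the next routine biopsy. These steps lower the risk. But the two reviews are there to confirm the listed criteria, which a participant with an uncovered event meets, and none of the steps states a hold.

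It can also be said that section 5 accepts controlled arrhythmia, old stroke and remote cardioversion from any cause, so the 60-day window is a clinical threshold. That is fair for general history. It is less persuasive for an event within 30 minutes of the agent that may be given again.

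The risk is limited in other ways. The cited cases involved bleeding or injured airways, lower absorption is expected in prophylactic use, and the study dose is below the rescue maximum. The amount of re-entry is also unclear: the front matter plans 100 participants and the Overview 100 procedures, about one each if read literally, although the consent section foresees repeats. These points bear on size and do not supply the missing rule.

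**Conclusion.** The point holds in limited form. Re-entry with fresh randomisation is expected, and no eligibility criterion addresses a safety outcome after an earlier study instillation as such. A reader might infer that no safety outcome bars re-entry. The documents do not support that: 5.2, 5.7, 5.12 and 5.16 catch several, and 5.8 may catch ectopy. The gap is the remaining events in the table, together with cardioverted ventricular arrhythmia once 60 days have passed.

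A reader might also take the spacing of the interim safety reviews as a measure of the risk. Data Monitoring describes those as trial-level analyses and does not present them as clearance of individuals, so their timing does not measure it.

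The expected number affected is small and cannot be computed from the documents. The 50% figure assumes fair, independent tosses; the 29 to 32 days assume the routine surveillance interval, whereas clinically prompted biopsies may come sooner. The change is worth making because the events are serious, the criteria as written readmit the participant, and one line closes the gap.

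**What to change.** Add exclusion 5.19, parallel to 4.13, and name it as an item to check at the Initial Evaluation chart review and the day-0 review. A participant who had any of the following within 30 minutes of an earlier study instillation is not randomised again unless the independent physician reviewer already named under Data Monitoring has documented clearance:

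- a cardiovascular event in safety item 2;
- acute closed-angle glaucoma (item 3);
- new ischemic ST change, ventricular tachycardia, supraventricular arrhythmia, bundle branch block, or second- or third-degree atrioventricular block (item 4).

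Leave ectopy under 5.8, and clarify there that documentation before the procedure includes an earlier study procedure. Transient heart-rate and blood-pressure changes (items 5 and 6) stay outside the hold. The amendment should say whether the reviewer sees the earlier assignment, since the only unmasking route now described is for emergency care.

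The hold applies to study randomisation only; the clinically indicated biopsy and rescue treatment are unaffected. It therefore does not protect against rescue epinephrine. The cost is a short amendment, occasional case reviews for the reviewer, and a few repeat procedures delayed or lost from the 100. Some of those will follow placebo, because sedation itself can cause arrhythmia.
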